3. ENDPOINTS AND BASELINE VARIABLES: DEFINITIONS AND CONVENTIONS

3.1. Primary Endpoints

3.1.1. Primary Efficacy Endpoints – Infant Participants

- RSV-positive MA-LRTI (as confirmed by the EAC) occurring within 90 days, 120 days, 150 days, and 180 days after birth (see [Section 5.1](#) for sequence of testing across time points).
- Severe MA-LRTI due to RSV (as confirmed by the EAC) occurring within 90 days, 120 days, 150 days, and 180 days after birth (see Section 5.1 for sequence of testing across time points).

3.1.2. Primary Safety Endpoints – Infant Participants

- Specific birth outcomes.
- AEs from birth to 1 month of age.
- SAEs and NDCMCs from birth through 6 months of age.
- SAEs and NDCMCs from birth through 12 months of age.
- SAEs and NDCMCs from birth through 24 months of age (for infants born to maternal participants enrolled during the first year of the study).

3.1.3. Primary Safety Endpoints – Maternal Participants

- Prespecified local reactions within 7 days after vaccination.
- Prespecified systemic events within 7 days after vaccination.
- AEs from the time of vaccination through 1 month after vaccination.
- SAEs throughout the study (through the 6-month-postdelivery study visit).

3.2. Secondary Endpoints

3.2.1. Secondary Efficacy Endpoints – Infant Participants

- Hospitalization due to RSV (as confirmed by the EAC) occurring within 90 days, 120 days, 150 days, 180 days, and 360 days after birth.
- MA-LRTI due to any cause with protocol-defined criteria occurring within 90 days, 120 days, 150 days, 180 days, and 360 days after birth.
- RSV-positive MA-LRTI occurring within 210 days, 240 days, 270 days, and 360 days after birth.

3.3. Other Endpoints

3.3.1. Exploratory Endpoints – Infant Participants

- RSV-positive MA-RTI (as confirmed by the EAC) occurring within 90 days, 120 days, 150 days, and 180 days after birth.
- RSV-positive MA-RTI occurring 181 to 730 days after birth.
- Incidence of all-cause MA-RTIs up to 730 days after birth.
- MA-LRTIs due to RSV occurring 361 to 730 days after birth.

- Severe MA-LRTIs due to RSV occurring 181 to 730 days after birth (as confirmed by the EAC).
- Hospitalization due to RSV occurring 181 to 730 days after birth (as confirmed by the EAC).
- MA-LRTIs due to any cause occurring 181 to 730 days after birth.
- RSV subgroup A– and subgroup B–specific MA-LRTI.
- Positivity for non-RSV respiratory pathogens obtained at unplanned MA-RTI visits.
- RSV A and RSV B serum neutralizing titers measured at birth.
- Primary and secondary efficacy by select demographic risk factors (eg, breastfeeding, maternal smoking, number of household members).
- Univariate summaries of healthcare utilization variables, which may include the following: number and type of medical visits, length of hospital stay, requirement for mechanical ventilation, requirement for respiratory diagnostic procedures, requirement for IV fluids, requirement for prescriptions, and antibiotic use.
- IgG concentrations against prefusion F measured at birth.
- MA-RTI, MA-LRTI, and severe MA-LRTI due to RSV occurring 0 to 730 days after birth in premature infants <37 weeks of age.

3.3.2. Exploratory Endpoints – Maternal Participants

- The incidence of all-cause MA-RTIs from vaccination up to 180 days after delivery.
- RSV A and RSV B serum neutralizing titers and prefusion F IgG titers measured before vaccination and at the delivery visit.
- Ig concentrations against nonvaccine RSV antigens measured before vaccination and at delivery visit.

3.4. Baseline Variables

3.4.1. Baseline Variables – Infant Participants

Day 1 is defined as the day of birth (Visit 1) for the infant participants.

Day 1 is considered the baseline visit for the following assessments in infant participants: immunogenicity (cord blood sample collected at birth), physical examination, and vital signs.

3.4.2. Baseline Variables – Maternal Participants

Day 1 is defined as the day of vaccination for the maternal participants. Day 1 is considered the baseline visit for the maternal immunogenicity assessments.

Day 1 is the start of the reporting period for local reactions/systemic events. For prespecified systemic events, a baseline assessment related to the 1-week period prior to vaccination will also be recorded in the e-diary.

3.5. Safety Endpoints

3.5.1. Adverse Events

AEs will be captured and reported in accordance with Pfizer reporting standards.

The time period for actively eliciting and collecting AEs and SAEs (“active collection period”) for each maternal participant, including her fetus, begins from the time the maternal participant or her parent(s)/legal guardian (if a minor) provides informed consent, which is obtained before participation in the study (ie, before undergoing any study-related procedure and/or receiving investigational product), through and including a minimum of 28 calendar days after the last administration of the investigational product.

In this study, the investigator and site staff will ensure the active elicitation and collection of nonserious AEs from informed consent through a minimum of 28 calendar days after vaccination. The active collection period for SAEs begins once informed consent has been provided until the maternal participant completes the study. In addition, AEs occurring up to 48 hours after blood draws that are related to study procedures must be reported in the CRF. Details of any MA-RTI will not be collected as an AE/SAE from informed consent until the maternal participant completes the study, unless the investigator or an appropriate designee deems the event to be possibly related to the investigational product. For maternal participants who are screen failures, the active collection period ends when screen failure status is determined.

For the infant participant, the time period for actively eliciting and collecting nonserious AEs begins at birth and continues through and including a minimum of 28 calendar days after birth. The active collection period for NDCMCs and SAEs begins at birth and continues through the last study visit. Details of any MA-RTI will not be collected as an AE/SAE from 72 hours after birth until the infant participant completes the study, unless the investigator or an appropriate designee deems the event to be possibly related to the investigational product or if it ends in death. In addition, AEs occurring up to 48 hours after blood draws or nasal swabs that are related to study procedures must be reported in the CRF.

During the active collection period, both nonserious AEs and SAEs are recorded on the CRF and will be categorized according to the current version (at the time of reporting) of MedDRA.

An immediate AE is defined as any AE that occurred within the first 30 minutes after administration of the investigational product for maternal participants.

An NDCMC is defined as a disease or medical condition, not previously identified, that is expected to be persistent or otherwise long-lasting in its effects.

An ADE is defined as an AE related to the use of an investigational medical device. These events will be captured separately and reported in relation to the administration of the investigational product.

A 3-tier approach will be used to summarize AEs for maternal participants and infant participants. Under this approach, AEs are classified into 1 of 3 tiers. Different analyses will be performed for different tiers (see [Section 6.6.1](#)).

Tier 1 events: These are prespecified events of clinical importance and are maintained in a list in the product's Safety Review Plan. There are currently no Tier 1 events defined.

Tier 2 events: These are events that are not Tier 1 but are “common”. A MedDRA PT is defined as a Tier 2 event if there are at least 1% in at least 1 group.

Tier 3 events: These are events that are neither Tier 1 nor Tier 2 events.

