2.1.4.3. Primary Safety Estimands – Maternal Participants

- Percentage of maternal participants reporting prespecified local reactions.**

This estimand includes the following 4 attributes:

- Population: Maternal participants who receive 1 dose of investigational product.
- Variable: Presence/absence of prespecified local reactions within 7 days after vaccination.
- Intercurrent event(s): For participants who discontinue, all collected data will be included; missing data will not be imputed.
- Population-level summary: Percentage of maternal participants reporting local reactions in each group.

- Percentage of maternal participants reporting prespecified systemic events.**

This estimand includes the following 4 attributes:

- Population: Maternal participants who receive 1 dose of investigational product.
- Variable: Presence/absence of prespecified systemic events within 7 days after vaccination.
- Intercurrent event(s): For participants who discontinue, all collected data will be included; missing data will not be imputed.
- Population-level summary: Percentage of maternal participants reporting systemic events in each group.

- Percentage of maternal participants reporting AEs from the time of vaccination through 1 month after vaccination.**

This estimand includes the following 4 attributes:

- Population: Maternal participants who receive 1 dose of investigational product.
- Variable: Presence of AEs within 1 month after vaccination.
- Intercurrent event(s): For participants who discontinue, all collected data will be included; missing AE dates will be imputed as described in Pfizer's Vaccine Statistics Rulebook.
- Population-level summary: Percentage of maternal participants reporting AEs through 1 month after vaccination in each group.

- **The percentage of maternal participants reporting SAEs throughout the study.**

This estimand includes the following 4 attributes:

- Population: Maternal participants who receive 1 dose of investigational product.
- Variable: Presence/absence of SAEs throughout the study.
- Intercurrent event(s): For participants who discontinue, all collected data will be included; missing AE dates will be imputed as described in Pfizer's Vaccine Statistics Rulebook.
- Population-level summary: Percentage of maternal participants reporting SAEs throughout the study in each group.

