6.1.2.3. SAEs and NDCMCs From Birth Through 6 and 12 Months of Age

- Analysis set: Safety – infant ([Section 4](#)).
- Analysis methodology: Descriptive summary statistics.
- Intercurrent events and missing data: For participants who discontinue, all collected data will be included; missing AE dates will be imputed as described in Pfizer’s Vaccine Statistics Rulebook.
- For each group, the number of participants with SAEs and NDCMCs through 6 and 12 months of age (n), percentage, and 95% CI will be presented (in separate outputs) for any event, each SOC, and each PT within each SOC, by vaccine group.

6.1.2.4. SAEs and NDCMCs From Birth Through 24 Months of Age (for Infants Born to Maternal Participants Enrolled During First Year of the Study)

- Analysis set: Safety – infant ([Section 4](#)).
- Analysis methodology: Descriptive summary statistics.
- Intercurrent events and missing data: For participants who discontinue, all collected data will be included; missing AE dates will be imputed as described in Pfizer’s Vaccine Statistics Rulebook.

- For each group, the number of participants with SAEs and NDCMCs (in separate outputs) through 24 months of age (n), percentage, and 95% CI will be presented for any event, each SOC, and each PT within each SOC, by vaccine group.
- For each group, the number of participants with SAEs and NDCMCs (in separate outputs) between 12 and 24 months of age (n), percentage, and 95% CI will be presented for any event, each SOC, and each PT within each SOC, by vaccine group.

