6.3.2. Exploratory Endpoints: Maternal Participants

6.3.2.1. Incidence of All-Cause MA-RTIs From Vaccination Up to 180 Days After Delivery

- Analysis set: Safety – maternal ([Section 4](#)).
- Analysis methodology: Descriptive summary statistics for all-cause MA-RTI up to 180 days.
- For each group, the number (n), percentage, and 95% CI of MA-RTI all-cause cases occurring up to 180 days will be presented.

6.3.2.2. RSV A and RSV B Serum Neutralizing Titers Measured Before Vaccination and at Delivery Visit

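### Maternal respiratory illness judged unrelated is kept out of AE/SAE collection, with no exception for death, so the primary maternal SAE endpoint can miss serious and fatal events

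*SAP*

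**What the plan says.** Section 3.5.1 sets the maternal SAE collection period: "The active collection period for SAEs begins once informed consent has been provided until the maternal participant completes the study". It then carves out one class of event over the same period: "Details of any MA-RTI will not be collected as an AE/SAE from informed consent until the maternal participant completes the study, unless the investigator" or a designee "deems the event to be possibly related to the investigational product. For maternal participants who are screen failures". The second quote shows where the maternal sentence stops: possible relatedness is its only exception.

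The infant sentence, in the next paragraph, starts its carve-out 72 hours after birth. It lifts the carve-out when the investigator or designee "deems the event to be possibly related to the investigational product or if it ends in death".

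Section 3.1.3 lists as a primary maternal safety endpoint "SAEs throughout the study (through the 6-month-postdelivery study visit". The estimand in Section 2.1.4.3 is given as "Variable: Presence/absence of SAEs throughout the study". Section 6.1.3.4 tabulates that endpoint for any event, by system organ class and by preferred term. None of these three places mentions that MA-RTIs have been removed.

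Maternal MA-RTIs have one analysis of their own, the exploratory summary in Section 6.3.2.1: "the number (n), percentage, and 95% CI of MA-RTI all-cause cases occurring up to 180 days will be presented".

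**The concern.** The endpoint's label and its content differ. A reader of the maternal SAE table would take it as complete, yet whether a serious respiratory illness is in it depends on an investigator's causality opinion. An SAE table by randomized group is useful largely because it shows imbalances without relying on that opinion.

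The usual reason for keeping respiratory illness out of AE data is that it is an efficacy endpoint and is adjudicated and reported as such. That reason fits the infants. It is weak for the mothers: their MA-RTIs are a descriptive exploratory endpoint, and the SAP specifies no maternal adjudication and no maternal efficacy test. The authors saw that a fatal infant respiratory illness belongs in the safety data, and they give no reason for treating a fatal maternal one differently.

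At stake is whether a maternal death or hospitalization for respiratory illness is visible, by group, in the primary maternal safety output.

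**Working it through.** The plan states no figure on this point, so the check sets the sections side by side.

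**1. The two collection rules (Section 3.5.1)**

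| | Mothers | Infants |
|---|---|---|
| Events removed | any MA-RTI | any MA-RTI |
| Start of removal | informed consent | 72 hours after birth |
| End of removal | study completion | study completion |
| Kept if possibly related | yes | yes |
| Kept if fatal | no | yes |

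The maternal removal runs from consent to completion, which is exactly the maternal SAE collection period. No part of that period is unaffected.

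**2. How severe a removed event can be (Section 5.4.2, Table 9).** A maternal medically attended visit may be an inpatient or emergency room visit. One listed symptom makes it an MA-RTI, and new or increased shortness of breath is on the list. Nothing in the definition caps severity.

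**3. One case traced through the plan.** A mother is admitted with new shortness of breath, the investigator judges the illness unrelated, and she dies.
- Table 9: the event is an MA-RTI.
- Section 3.5.1: it is not collected as an AE or SAE. The same outcome in an infant older than 72 hours would be collected.
- Section 6.1.3.4: she is not in the numerator on account of this event.
- Section 6.1.3.3: if the illness falls within 1 month after vaccination, it is missing from that AE table as well.

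**4. Where else the event could appear**
- Section 6.3.2.1: counted as an MA-RTI, with no seriousness or outcome.
- Section 6.6.1: the listings cover reported AEs, and this event was not reported as one.
- Section 6.5.2: a death may show as a withdrawal reason, but not as an SAE with a class and term.
- Sections 3.6.1 and 6.3.1.11: hospital and intensive care use is analyzed for infants only.
- No summary of maternal deaths is specified.

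**5. Size.** For the any-SAE row, the number of women missed would be

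N × P(serious or fatal MA-RTI) × P(judged unrelated, given that) × P(no other SAE, given both).

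Section 2.2 gives the planned N, 6,900 to 10,000. None of the three probabilities is in the SAP, so the product cannot be evaluated. Only the weight of one missed woman follows from the design. With 1:1 randomization a group has about 6,900/2 = 3,450 to 10,000/2 = 5,000 women, so one woman is 1/3,450 = 0.029% to 1/5,000 = 0.020% of a group. A few omissions would hardly move the overall SAE percentage. They would matter in the rows for deaths and serious respiratory events, where single cases are the information.

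**The case against.** The strongest reply is that AE reporting rules belong to the protocol, and that Section 3.5.1 itself opens by deferring to the sponsor's reporting standards. Those sources are not at hand and may require fatal events to be reported by another route. This limits what can be said about actual practice. It does not remove the inconsistency, because the SAP states the rule itself and its endpoint wording does not match it.

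The relatedness exception is real, and in a double-blind trial it is applied without knowledge of group. So the rule does not obviously favor one arm, but the count is still incomplete. Maternal SAEs are also summarized descriptively, and Section 6.6.1 calls safety analysis generally exploratory. No hypothesis test or efficacy decision depends on this point.

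Three stronger readings are tempting and are not supported.

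- A reader might infer that a maternal death would be invisible. It would not: the illness is in the MA-RTI count, withdrawals are tabulated and listed with reasons, and an external monitoring committee follows safety. What is missing is the event as an SAE in the primary table.
- A reader might infer the same gap for infants, since non-fatal unrelated respiratory illness after 72 hours is also absent from the SAE tables, in which "the number of participants with SAEs and NDCMCs through 6 and 12 months of age (n), percentage, and 95% CI will be presented". Fatal infant cases are kept, however, and serious ones are reported by group elsewhere: severe RSV illness (Sections 6.1.1.2 and 6.3.1.5), RSV hospitalization, with a separate analysis of cases admitted to intensive care (Sections 6.2.1.1 and 6.3.1.6), all-cause lower respiratory illness (Sections 6.2.1.2 and 6.3.1.7), and visit setting and ventilation in the infant safety set (Section 6.3.1.11). Section 6.6.6 adds a summary of specific diagnoses.
- A reader might attach a number of missed deaths or hospitalizations, or cite the pandemic to suggest a large one. The SAP gives no maternal rates, and Section 2.2 mentions COVID-19 only in connection with RSV case accrual and sample size.

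**Conclusion.** The point holds for mothers. As written, a fatal or otherwise serious maternal MA-RTI not judged possibly related is left out of a primary safety endpoint whose definition, estimand and analysis announce no such omission. The maternal and infant rules differ on death without explanation. No specified output restores the event as an SAE.

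The conclusion assumes that sites follow Section 3.5.1 literally and that no unseen rule overrides it. The size of the undercount is unknown and may be small. The direction is clear: the maternal SAE count, and the 1-month AE count, can only be too low.

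**What to change.** 1. In Section 3.5.1, reconcile the maternal and infant sentences by giving the maternal rule the same exception for death. If the protocol carries the same maternal sentence, change it to match.
2. In Section 6.1.3.4, add a tabulation by group, in the Safety – maternal set, of fatal and serious (for example hospitalized) maternal MA-RTIs, alone and combined with SAEs, as far as the collected MA-RTI data allow.
3. Footnote the SAE table with any MA-RTIs that remain excluded. The 1-month AE table in Section 6.1.3.3 needs the same note.

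The cost is a few more SAE reports and one extra table. One practical limit applies: this SAP version dates from September 2022, after the April 2022 interim analysis that Section 7.2 describes, so events already recorded under the present rule may lack seriousness or outcome. The table should then say for how many women that information is missing.

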3.5.2. Reactogenicity Data

Reactogenicity data are prompted AEs collected using an e-diary, during Days 1 through 7 in maternal participants, starting on the day of vaccination (Day 1). The reactogenicity data will include local reactions (redness, swelling, and pain at the injection site) and systemic events (fever, fatigue, headache, vomiting, nausea, diarrhea, muscle pain, and joint pain). Prior to vaccination, a baseline assessment of prespecified systemic events will also be recorded in the e-diary.

3.5.2.1. Local Reactions

Local reactions reported in the e-diary are redness, swelling, and pain at the injection site.

Presence of Local Reactions (Proportion of Participants Reporting)

The participant or her parent(s)/legal guardian (if a minor) will record the presence or absence of pain at the injection site in the e-diary as “mild,” “moderate,” “severe,” or “none”. Redness and swelling will be measured and recorded in measuring device units (range: 1 to 20 and 21+) and then categorized during analysis as mild, moderate, or severe based on the grading scale in [Table 4](#). Measuring device units can be converted to centimeters according to the following scale: 1 measuring device unit = 0.5 cm. A participant with a severe (Grade 3 or above) local reaction will be prompted to contact the investigator to perform an unscheduled visit and assess the reaction.

Only an investigator is able to classify a maternal participant's local reaction as Grade 4, after clinical evaluation of the maternal participant or documentation from another medically qualified source (eg, emergency room or hospital record) or, in the case of pain at the injection site only, contact with the participant. If a maternal participant experiences a Grade 4 local reaction, the investigator must immediately notify the sponsor. Grade 4 reactions will be collected on the unscheduled reactogenicity page and as an AE on the CRF. The AE event will be graded using the AE intensity grading scale as indicated in the table "Assessment of Intensity" in [Section 10.2.4 of the protocol](#).

The presence or absence of each local reaction on a given day is defined as follows:

- = "Missing," if the value is missing on a given day.
- = "Yes," if the reaction is recorded as "yes" for redness or swelling with a diameter of >2.0 cm **or** "mild," "moderate," "severe," or "Grade 4" for pain at the injection site on a given day.
- = "No," if the reaction is recorded as "no" **or** as "yes" with a diameter of ≤ 2.0 cm for redness or swelling **or** "none" for pain at the injection site on a given day.

For each local reaction, the derivation of whether or not the specific reaction occurred on "any day (Day 1-7)" will be made. The derivation of this variable is given in Table 2 below.

Table 2. Derived Variables for Each Local Reaction

Variable ^a	Yes (1)	No (0)	Missing (.)
Any day (Day 1-7)	The reaction is reported as "yes" with a diameter of >2.0 cm for redness/swelling or "yes" for pain any day from Day 1 through Day 7.	The reaction is reported as "no" (or "yes" with a diameter ≤ 2.0 cm for redness/swelling) on all 7 days or as a combination of "No" and missing on all 7 days.	The reaction is reported as missing on all 7 days.

a. The variable will be defined for each of the 3 local reactions.

For "any local reaction" on any day, a similar definition can be applied as given in Table 3 below.

Table 3. Derived Variables for Any Local Reaction

Variable	Yes (1)	No (0)	Missing (.)
Any day (Day 1-7)	The reaction is reported as any redness or swelling >2.0 cm or "yes" for pain at injection site on any day during Days 1 through 7.	The reaction is reported as redness or swelling ≤ 2.0 cm or pain at injection site as "no" on all 7 days or as a combination of above and missing on all 7 days for all 3 local reactions.	All of the local reactions are reported as missing on all 7 days.

Grading Scale for Local Reactions

The grading of local reactions is listed below in Table 4.

Table 4. Grading Scale for Local Reactions

	Mild Grade 1	Moderate Grade 2	Severe Grade 3	Grade 4^a
Redness	>2.0 cm to 5.0 cm (5 to 10 measuring device units)	>5.0 cm to 10.0 cm (11 to 20 measuring device units)	>10 cm (>20 measuring device units)	Necrosis or exfoliative dermatitis
Swelling	>2.0 cm to 5.0 cm (5 to 10 measuring device units)	>5.0 cm to 10.0 cm (11 to 20 measuring device units)	>10 cm (>20 measuring device units)	Necrosis
Pain (at the injection site)	Does not interfere with activity	Interferes with activity	Prevents daily activity	Emergency room visit or hospitalization for severe pain at the injection site

a. Only an investigator is able to classify a maternal participant's local reaction as Grade 4, after clinical evaluation of the maternal participant or documentation from another medically qualified source (eg, emergency room or hospital record) or, in the case of pain at the injection site only, contact with the maternal participant or her parent(s)/legal guardian (if a minor). Grade 4 assessment should be made by the investigator using the AE severity grading scale. The assessment will be collected on the AE case report form.

Maximum Severity for Local Reactions

The maximum severity (highest grading) of each local reaction within 7 days after vaccination will be derived. The maximum severity will be derived as follows:

- = “Missing,” if values are missing for all days from Day 1 through Day 7.
- = 0, if all reactions are reported as “no” or a combination of missing and “no” for all days from Day 1 through Day 7.
- = *highest grade* (maximum severity) within 7 days after vaccination if the answer is not “no” for at least 1 day.

Duration of Each Local Reaction

The duration of each local reaction will be calculated in days as (resolution date of reaction - start date of reaction + 1). Resolution of the reaction is the last day on which the reaction is recorded in the e-diary or the date the reaction ends if it is unresolved during the participant diary recording period (end date collected on the CRF), unless chronicity is established. If there is no known end date, the duration will be considered unknown and set to missing.

Onset of Local Reaction

The onset day of each local reaction and any local reaction will be derived.

For the onset day of each local reaction, if the participant or her parent(s)/legal guardian (if a minor) report severity change of the local reaction, the first day of initial reporting of that specific local reaction will be counted.

For the onset day of any local reaction, the first day of reporting any severity of any local reaction will be counted.

In summary, the following variables will be derived for local reaction:

1. Presence or absence of each local reaction on each day (Days 1-7) after vaccination.
2. Presence or absence of each local reaction on “any day (Day 1-7)” after vaccination.
3. Presence or absence of any local reaction on “any day (Day 1-7)” after vaccination.
4. Maximum severity of each local reaction on “any day (Day 1-7)” after vaccination.
5. Duration of each local reaction after vaccination.
6. Onset day of each local reaction after vaccination.
7. Onset day of any local reaction after vaccination.

